**Study of Adoptive Transfer of Invariant Natural Killer T Cells
Combined With TAE/TACE to Treat Unresectable Hepatocellular
Carcinoma (HCC): Phase II Clinical Trial**

NCT04011033

October 1, 2017

1. Background and Aims

Hepatocellular carcinoma (HCC) is the fifth most common cancer and a leading cause of cancer-related death among males and females of all ages ¹. It was estimated that in 2018, there were 840 thousand new liver cancer cases and 780 thousand liver cancer-related deaths in the world ¹. Of importance, unresectable HCC accounts for more than 70%~80% of the cases, limiting the possibility of achieving a cure in many patients ^{2,3}. Currently, the prognosis of HCC is poor, with a 5-year survival of about 18% even in developed countries ⁴.

Transarterial embolization (TAE) or transarterial chemoembolization (TACE) is a standard therapy for intermediate-stage HCC, which is accepted as a routine practice worldwide ^{5, 6}. Nevertheless, different clinical characteristics of HCC, such as liver function and tumor load (different size, number, and location), will lead to different responses to TA(C)E treatment and different survival times. Furthermore, repeated TACE procedures could gradually lead to TACE refractoriness, and some patients even show TACE failure ⁷. According to the Japanese Society of Hepatology (JSH) guidelines ⁸, TA(C)E failure is defined as an insufficient response after ≥ 2 consecutive TA(C)E procedures, as revealed by the response evaluation using computed tomography (CT) or magnetic resonance imaging (MRI) after 1~3 months. The median tumor doubling time after an initial response of HCC to TACE is 46 days, and $>90\%$ of the recurrent nodules have a doubling time of <3 months ⁹. The recurrence rate of intrahepatic lesions after TA(C)E is 37% and 61% at 6 and 12 months, respectively ¹⁰. Therefore, patients with HCC failed to respond to TACE,

under which circumstance is defined as TACE refractoriness, should switch to or combine with systemic therapy as soon as possible because repeated TACE is no longer beneficial for such patients ⁹.

The Asia-Pacific region has the highest incidence of HCC, with >50% of all the cases in the world ¹. In addition, >80% of HCC cases in China occur due to viral hepatitis and cirrhosis ^{11, 12}. Of note, pancytopenia is a common clinical manifestation of liver cirrhosis ^{13, 14}. Therefore, the number and frequency of peripheral blood lymphocytes in many patients with HCC are lower than in the normal population ¹⁵. Furthermore, the decline of immune system function is the basis of the occurrence, development, recurrence, and metastasis of various tumors, including the decrease in anti-tumor killing and immune monitoring functions ¹⁶. TA(C)E can induce tumor necrosis, and ischemia-reperfusion injury can induce further tumor cell damage. TA(C)E is considered to improve tumor immunogenicity by releasing antigens and stimulating cytotoxic lymphocytes (CTL) recruitment in tumors ¹⁷. After reperfusion, natural killer T (NKT) cells are activated rapidly by CD1d ¹⁸. Invariant NKT (iNKT) cells are enriched in the human liver, and they express a limited T-cell receptor (TCR) β spectrum and unique TCR α rearrangement (V α 24-J α 18 in humans and V α 14-J α 18 in mice) ¹⁹. Clinical trials have shown that activated iNKT cells can rejuvenate depleted CD8 $^{+}$ T cells and natural killer (NK) cells ²⁰⁻²⁴. Some of these trials activated iNKT with aGalcer-loaded monocytic dendritic cell vaccines and others adoptively transferred iNKT cells. These activated or reactivated lymphocytes can help remove residual cancer cells and prevent tumor recurrence and metastasis. Therefore, TA(C)E

combined with adoptive iNKT therapy might be an option for the treatment of HCC.

In our previous phase I trial ²⁵, the adoptive transfer therapy of autologous iNKT cells in patients with recurrent or refractory Barcelona Clinic Liver Cancer (BCLC) B/C liver cancer demonstrated a partial clinical response and objective immune response, with very slight side effects. Therefore, we will conduct a multicenter, randomized, open trial in BCLC B/C stage patients with HCC after failure to TACE to explore the efficacy and safety of TAE combined with adoptive autologous iNKT cell therapy compared with TAE alone.

2. Study Design and Participants

This randomized, multicenter, open-labeled phase II trial will be conducted at Beijing YouAn Hospital of Capital Medical University, Beijing Shijitan Hospital of Capital Medical University, and Beijing Ditan Hospital of Capital Medical University between March 2018 and March 2020. This study will be performed according to the guidelines of the Helsinki Declaration.

3. Criteria

Inclusion Criteria:

1) 18-80 years of age, 2) TACE failure/refractory BCLC B HCC confirmed by CT, MRI, and/or histopathology, 3) life expectancy of at least 12 weeks, 4) Child-Pugh A/B, 5) adequate hematological and renal functions, including white blood cell (WBC) count $>3.0 \times 10^9/L$, lymphocyte count $>0.8 \times 10^9/L$, platelet count $>50 \times 10^9/L$, hemoglobin concentration $>85 \text{ g/L}$, and serum creatinine

concentration of <1.5-times the upper limit of normal value (ULN), and 6) previous treatment terminated at least 4 weeks before entry to this study.

Exclusion Criteria:

1) Known history of the human immunodeficiency virus (HIV) or syphilis infection, 2) clinically serious infections, 3) history of stem cell transplant or organ allograft, 4) history of severe hypertension or cardiac disease, 5) known central nervous system (CNS) tumor, 6) autoimmune disease requiring systemic therapy with immunosuppressive agents, 7) history of allergy to immunotherapy or related drugs, 8) pregnancy or lactation, or 9) deemed not suitable for cellular immunotherapy by the investigators.

Research Suspension / Termination Criteria:

1) the patient withdrew his informed consent and asked to withdraw, 2) CT/MRI examination confirmed the occurrence of PD, according to the imRECIST, 3) unable to tolerate AEs, or serious adverse events (SAE), abnormal laboratory tests or concurrent diseases, etc, and the researchers judged that it is not in the best interests of patients to continue to participate in the study, 4) the study and treatment of patients was significantly delayed for any reason, which exceeded the scheduled treatment time \geq 8 weeks from the time of the last administration, 5) other situations in which the researchers believe that it is necessary to stop treatment, 6) pregnancy occurred in the patient, 7) use new antineoplastic therapy, 8) the sponsor terminates the study.

Elimination Criteria:

1) the use of research drugs is not consistent with the clinical regimen, and has a significant impact on the evaluation of efficacy and safety, 2) those without any record, 3) those who did not take research drugs.

TACE Failure Criteria:

1) Intrahepatic lesion [i, two or more consecutive ineffective responses seen within the treated tumors (viable lesion >50%), even after changing the chemotherapeutic agents and/or reanalysis of the feeding artery, on response evaluation CT/MRI after 1–3 months following adequately performed selective TACE. ii, two or more consecutive progressions in the liver (including an increase in the number of tumors compared to that before the previous TACE procedure), even after changing the chemotherapeutic agents and/or reanalysis of the feeding artery, on response evaluation CT/MRI after 1–3 months following adequately performed selective TACE]. 2) Continuous elevation of tumor markers right after TACE, even though transient minor reduction is observed. 3) Appearance of vascular invasion. 4) Appearance of extrahepatic spread.

4. Endpoints and Definitions

The primary endpoint is the PFS, i.e., the time from enrollment to disease progression according to the modified RECIST (mRECIST) guideline in trial immunotherapeutics, or death from any cause, whichever occurred first. Secondary endpoints include overall survival (OS), objective response rate (ORR), disease control rate (DCR), quality of life (QoL), and safety. Patients without any post-baseline tumor assessment are considered non-responders. Objective responses

will be confirmed at least 28 days after the initial documentation of the response.

Progression-Free Survival: Time from the date of enrollment to the date of first documentation of tumor progression.

Progression was defined using Modified RECIST (mRECIST): an increase of at least 20% in the sum of the diameters of viable (enhancing) target lesions, taking as reference the smallest sum of the diameters of viable (enhancing) target lesions recorded since treatment started.

Overall survival: time from the date of enrollment to the date of death from any cause.

Objective response rate: including complete response (CR) and partial response (PR) evaluated by imaging according to mRECIST for target lesions and assessed by MRI/CT. Complete Response (CR), disappearance of any intratumoral arterial enhancement in all target lesions. Partial Response (PR), at least a 30% decrease in the sum of diameters of viable (enhancement in the arterial phase) target lesions, taking as reference the baseline sum of the diameters of target lesions. Objective Response Rate = CR + PR.

Disease Control Rate: including complete response (CR), partial response (PR), and disease stabilization (SD), evaluated by imaging according to mRECIST for target lesions and assessed by MRI/CT. Complete Response (CR), disappearance of any intratumoral arterial enhancement in all target lesions. Partial Response (PR), at least a 30% decrease in the sum of diameters of viable (enhancement in the arterial phase) target lesions, taking as reference the baseline sum of the diameters of target

lesions. Stable disease (SD), any cases that do not qualify for either partial response or progressive disease. Disease Control Rate = CR + PR + SD.

The Quality of Life (QoL) will be assessed according to the EORTC (EORTC: the European Organization for Research and Treatment of Cancer) QLQ-C30 scale between the TAE-iNKT and TAE group. And the time to deterioration of QoL, as reported by the patient, with deterioration defined as a decrease from baseline of 10 points or more on the EORTC QLQ-C30 maintained for two consecutive assessments.

Safety and side-effect profiles will be assessed based on the nature, frequency, and severity of adverse events, according to the National Cancer Institute (NCI) Common Terminology Criteria for Adverse Events (CTCAE), version 4.0.3. Common Adverse events (AEs) occurring on or after the first treatment day through the end of this trial will be recorded according to NCI-CTCAE 4.03.

5. Drugs for research

Name of Drug

iNKT cells

Production of iNKT Cells

- 1) Isolate PBMCs by leukapheresis using a COM.TEC apheresis system and Lymphoprep density gradient medium.
- 2) Resuspend PBMCs in Corning serum-free cell medium KBM581 and stimulate with 100 ng/mL α -GalCer and 100 U/mL animal-free recombinant human

interleukin-2 for 48 hours; the rhIL-2 was replenished every other day.

3) Stimulate PBMCs with 1,000 IU/mL granulocyte-macrophage colony-stimulating factor and IL-4 for 1 week, and obtain mature, monocyte-derived DCs.

4) Sort iNKT cells by using anti-iNKT microbeads according to the manufacturer's protocol on day 7.

5) Co-culture the sorted iNKT cells with mature DCs for 14 days, and collect cells for infusion on day 21. An aliquot of cells was used for immunophenotyping and functional testing.

6) Determine the frequency of iNKT cells in T cells by using a FACSCanto II cytometer.

7) The criteria for iNKT cell administration include a negative bacterial culture, a negative mycoplasma test result, and an endotoxin level < 0.05 units/mL.

Production Standards

Inspection item	Statutory (Pharmacopoeia) standard	Internal quality control standard
Color	---	Colorless or innocent
Character	---	Transparent suspension
Identification	Flow cytometry	Cellular immunophenotype
Rate of survival cell	≥95%	≥95%
Quantity (survival cell)	---	Day 7: $\geq 5 \times 10^7$; Day 21: $\geq 1 \times 10^8$
Microbial limit test	Aseptic, (bacteria and mold shall not be detected).	Aseptic, (bacteria and mold shall not be detected).

	Mycoplasma (not allowed to be detected). Endotoxin≤2EU/ml	Mycoplasma (not allowed to be detected). Endotoxin≤2EU/ml
Proportion	90%	90%

Dose and Administration

Intravenous infusion. From the date of cell collection, the cells will be infused on the 7th and 21st day of each month as a course of treatment for a total of three courses, the reinfusion dose is determined according to the patient's body surface area, which was about $10^8\sim10^9$ cells/ m^2 .

Drug Combination

Human IL-2 (25,000 IU/kg per day) will be administered (subcutaneous injection) once every other day for 1 week after iNKT cell infusion.

6. Interventions

The patients will be randomized 1:1 using a random number table to receive TAE treatment vs. the combination treatment of TAE and adoptive autologous iNKT cell infusion (TAE-iNKT). The patients in the TAE and TAE-iNKT groups will undergo TAE at weeks 0 and 4 after enrollment. TAE will be performed at the local hospitals.

In the TAE-iNKT group, iNKT cells will be administered at 1st, 3th, 5th, 7th, 9th, 11th weeks after enrollment. After iNKT cell infusion, a subcutaneous injection of interleukin (IL)-2 (25,000 IU/kg) will be administered once every other day for 1 week.

All target and non-target lesions will be assessed by chest, abdomen, and pelvis CT or MRI at baseline and every 4 weeks until week 16, and then every 8 weeks until

radiological progression. At the same time points, routine blood tests, tumor biomarkers, α -fetoprotein (AFP), and quality of life (QoL) will be measured.

After the end of treatment, the survival follow-up of the subjects will continue to be conducted every 3 months, while those who end treatment for reasons other than disease progression will undergo regular tumor imaging evaluation as much as possible after treatment, and survival follow-up must be carried out.

The details of follow-up are shown in the table below:

Project / time	Screening/ baseline period (-14d~0w)	The first cycle 3W \pm 7d	The second cycle 6w \pm 7d	Odd cycle \pm 7d	Even cycle \pm 7d	Out-of- group follow-up \pm 7d
Sign the informed consent form	×					
Medical history	×					
Inclusion / exclusion criteria	×					
Physical examination and vital signs	×	×	×	×	×	×
Blood routine	×	×	×	×	×	×
Urine routine	×	×	×	×	×	×
Biochemistry (liver and kidney function, blood glucose, blood lipid)	×	×	×	×	×	×
Myocardial enzyme	×	×	×	×	×	×
Thyroid function	×	×	×	×	×	×
Five items of hepatitis B	×					
Hepatitis C antibody	×					
HBV-DNA/HCV RNA quantification	×		×		×	×
Syphilis antibody	×					
HIV antibody	×					
Digestive tumor markers, AFP	×	×	×	×	×	×
Coagulation	×	×	×	×	×	×

Autoantibody	×					
T cell subsets	×	×	×	×	×	×
Detection of cell suspension (bacteria, fungi, endotoxin)	×	×	×	×	×	
Electrocardiogram	×		×		×	×
Colour Sonography	×					×
Liver enhanced MR or CT	×		×		×	×
Imaging data of other organs	×		×		×	×
Pathological examination of tumor	×					
Drug combination	×	×	×	×	×	×
Adverse events	×	×	×	×	×	×

The Implementation of TAE

- 1) Select catheterization of the feeding artery by using a microcatheter.
- 2) Perform abdominal and hepatic arteriography.
- 3) Embolization with Gelfoam until near stasis of the arterial flow.
- 4) Determine the dose of iodized oil by the tumor size or based on whether the portal vein had a tumor thrombosis.
- 5) Inject the emulsion of iodized oil until the accumulation of the emulsion in the tumor and the visualization of the portal vein branches near the tumor. (If there was a significant arteriportal shunt, embolization with Gelfoam was first performed to occlude the shunt, after which the iodized oil emulsion was infused, and embolization with Gelfoam was performed.)

7. Statistical Analysis

The trial was designed to use a 2-sided 5% type I error and had 80% power to detect an improvement in PFS from 1.5 months in the TAE group to 4.5 months in the TAE-iNKT group, corresponding to a hazard ratio (HR) of 0.33 in terms of median PFS. In consideration of these assumptions, the trial design was powered for 60 patients to be randomly assigned in each group as the intention-to-treat population (allocation ratio of 1:1, n=30 patients in each group), and allowing for a drop-out rate of 20%. Sample size estimation was performed using PASS 11.

Continuous variables will be expressed as the median and IQR, and will be compared using t tests or Mann-Whitney tests. Categorical variables will be presented as the frequency and percentage, and will be compared using Fisher's exact tests. Survival and time to QoL deterioration will be estimated using the Kaplan-Meier method, and their 95% CIs will be calculated using the Brookmeyer and Crowley method. Survival differences will be compared using log-rank tests. Peripheral blood cells will be analyzed using Sidak's multiple comparison test. The overall two-sided significance level of $P < .05$ will be split into a two-sided significance level of $P < .01$ for tests of PFS, OS, ORR, DCR, and QoL according to the Bonferroni method (dividing the available total α (typically 0.05) equally among the chosen endpoints). If the PFS and/or all secondary endpoints are statistically significant at a two-sided significance level of 0.01, the curative effect of TAE-iNKT will be deemed better than that of TAE alone. All statistical analyses will be conducted using SAS software version 9.4 (SAS Institute).

8. Data Management.

Designated and trained staff act as data managers, responsible for the data management of this study, complete data collection, input, quality inspection and make data security monitoring plan in accordance with the requirements of GCP. When the following conditions are met, the data can be locked: all data have been entered into the database; all questions have been solved; the researcher has completed the signature; the analytical population has been defined and judged. After the database is locked, if the project team evaluates that it needs to be unlocked, it can reopen the lock. The process of unlocking the database should include notifying the project team, clearly defining which data errors will be changed, the reason for the change, and the date of the change, and signed by key researchers, data managers, and statistical analysts. The re-locking of the database should follow the same notification / approval process as the database lock for the first time.

9. Handling of Adverse Events during and after the Study.

Researchers should follow up, observe and record the outcome of all adverse events, and follow patients who drop out of the study because of adverse events until the adverse events are completely relieved. Researchers must determine whether adverse events are related to research drugs and provide evidence to support this judgment.

In all clinical or laboratory examinations, abnormal items of clinical significance should be filled in the form of adverse events and followed up at least once a week until normal or reached the baseline level.

Measures to Deal with Expected Adverse Events

- 1) Fever: patients may have different degrees of fever, doctors will give symptomatic antipyretic treatment.
- 2) Allergic reaction: a small number of patients may have allergic reaction, such as skin pruritus, urticaria, chest tightness and so on.
- 3) Digestive tract symptoms: patients may have digestive tract symptoms of nausea, vomiting and various stomach discomfort, and doctors will give gastric mucosal protective agents, acid suppressants, gastric motility drugs or antiemetic drugs according to the situation.

If any serious adverse event occurs in the course of clinical research, the researcher shall report the serious adverse event to the ethics committee of the research unit and the applicant unit of clinical research within 24 hours of knowing the serious adverse event. At the same time, researchers must fill in the form of serious adverse events and record the time, severity, duration, measures taken and outcome of serious adverse events.

10. Follow-up and Medical Measures after the End of the Study.

After the completion of this study, the subjects may still have the end events of the disease itself, such as the progression of liver cancer and the deterioration of liver function. We will closely observe and follow up, communicate with patients in time, and put forward objective medical suggestions. Therefore, the regular return visit of the subjects will be very important, because it will help to detect the progress of these

diseases in the early stage, so that the clinical follow-up doctors can take timely and effective treatment measures to improve the prognosis.

11. Data Preservation.

The original data of the examination results (including the test sheet) are owned by the researchers. The CRF shall be in triplicate, one copy shall be retained by the bidding unit, one copy by the participating unit and one copy by the statistical unit. Demographic data, related medical history, physical examination, a series of laboratory tests and combined medication and adverse events take the CRF table and hospital case system data as the original data, in which the part related to the privacy of the subjects is only reflected in the original medical records.

Researchers should properly preserve research documents in accordance with relevant requirements. Important documents should be kept until 5 years after the end of the clinical study.

12. References

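### The elimination criteria can remove randomised patients from the TAE-iNKT arm only, and nothing keeps those patients in the primary analysis

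*Combined protocol and SAP*

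**What the plan says.** Section 3 has a short list headed Elimination Criteria. Criterion 1 applies where "the use of research drugs is not consistent with the clinical regimen, and has a significant impact on the evaluation of efficacy and safety". Criterion 2 covers patients with no record. Criterion 3 covers "those who did not take research drugs".

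The section headed "5. Drugs for research" names iNKT cells as the drug and lists IL-2 as its companion. TAE is not listed there; it appears in Section 6 as a procedure given to both arms at weeks 0 and 4. On the cells, Section 6 says: "In the TAE-iNKT group, iNKT cells will be administered at 1st, 3th, 5th, 7th, 9th, 11th weeks after enrollment". The control arm receives neither cells nor IL-2.

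Infusion depends on the product passing release tests. Section 5 states: "The criteria for iNKT cell administration include a negative bacterial culture, a negative mycoplasma test result, and an endotoxin level" below a set limit. The production table adds minimum viable cell counts at day 7 and day 21.

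The intention-to-treat population is mentioned once, in the sample-size sentence of Section 7. Section 8 makes it a condition of database lock that the analytical population has been settled, but gives no rule for settling it. Section 2 describes the trial as open-label.

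**The concern.** Criteria 1 and 3 depend on a product that one arm receives. Taken literally, criterion 3 eliminates every control patient, which cannot be intended. The workable reading is that criteria 1 and 3 act on TAE-iNKT patients alone; only criterion 2 can apply to both arms. The plan itself supplies a route out of that arm. A patient whose autologous product fails release is never infused (criterion 3) or receives fewer infusions than planned (possibly criterion 1). A control patient with the same prognosis has no such exit, so the arms stop being comparable as randomised.

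A link between failed production and prognosis is plausible but not proven. Section 1 says that "the number and frequency of peripheral blood lymphocytes in many patients with HCC are lower than in the normal population", and that "the decline of immune system function is the basis of the occurrence, development, recurrence, and metastasis of various tumors". Patients who yield too few cells may therefore also be those who progress early.

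The population can also be settled with outcomes in view. Criterion 1 turns on impact on the efficacy evaluation, the trial is open-label, Section 8 sets database lock as the only deadline, and nobody is named to judge eligibility blind to outcome. Under the Section 7 decision rule, significance on PFS alone can suffice for a claim of superiority, so a false PFS win is a false trial success.

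**Working it through.** **Plan's own figure.** The plan gives no elimination rate, so there is none to reproduce. The arm size used is 30, from the Section 7 allocation statement. As a check on that size, Freedman's formula with HR 1/3, two-sided 0.01 and 80% power gives (2.576 + 0.842)² × ((1 + 1/3)/(1 − 1/3))² = 11.68 × 4 = 46.7, so 47 events. Then 47/0.8 = 58.75, so 59 patients, or 60 when rounded per arm. The 5% level stated for the sample size would give only 33 to 40. That mismatch is a separate matter and does not affect what follows.

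**Inputs from the documents.** 30 per arm; control median PFS 1.5 months (Section 7), here used in both arms so that there is no true effect; PFS test at two-sided 0.01 (Section 7); scans at weeks 4, 8, 12 and 16, then every 8 weeks (Section 6).

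**Assumed inputs.** The number removed, the hazard multiples, exponential PFS times and no other censoring.

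**Early-event arithmetic.** The median is 1.5 × 4.345 = 6.52 weeks.
- P(event before week 1) = 1 − 0.5^(1/6.52) = 10.1%, or 3.0 of 30.
- P(no event by week 4) = 0.5^(4/6.52) = 65.4%, or 19.6 of 30.

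**Simulation.** 10,000 runs per scenario (Monte Carlo SE about 0.1 to 0.2 percentage points), removing patients from the TAE-iNKT arm only. The log-rank statistic is Z = (O − E)/√V, and a false iNKT win is Z < −2.576. The apparent HR is the geometric mean of exp[(O − E)/V].

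| Removed from TAE-iNKT | False win, exact times | False win, scan schedule | Apparent HR (exact / scan) |
|---|---|---|---|
| none | 0.7% | 0.6% | about 1.0 |
| earliest 1 | 1.0% | 0.8% | not tabulated |
| earliest 2 | 1.6% | 1.3% | not tabulated |
| earliest 3 | 1.8% | 1.6% | 0.90 / 0.89 |
| earliest 6 | 4.7% | 4.6% | 0.80 / 0.77 |
| 3 or 6 at random | 0.4–0.6% (both time scales) | | about 1.0 |
| 3 longest PFS times | bias reversed | | 1.38 / 1.45 |

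Repeat runs of the same model gave 1.4% to 2.2% for the earliest 3 and 3.8% to 4.8% for the earliest 6. Removing exactly those with an event before week 1 gives 1.6% (HR 0.90 exact, 0.88 on the scan schedule).

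**Milder mechanism.** The same share of higher-hazard patients is placed in both arms, the overall median is held at 6.52 weeks, and these patients are removed from TAE-iNKT only.
- 10% uninfused at 2 to 3 times the hazard: 1.0–1.3%, HR 0.91–0.95.
- 20% uninfused at 2 to 3 times the hazard: 1.3–2.0%, HR 0.84–0.90.

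**Response endpoints.** If those removed are non-responders, the TAE-iNKT ORR is multiplied by 30/27 = 1.11 (3 removed) or 30/24 = 1.25 (6 removed). If DCR were read at the week-4 scan and those removed had already progressed, it would move from 19.6/30 = 65% to 19.6/27 = 73% or 19.6/24 = 82%. The plan does not fix DCR at week 4; this is an illustration. OS and QoL were not computed.

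**The case against.** **Research drugs may mean assigned treatment.** Because the literal reading is absurd, the term might include TAE, and then either arm could lose patients. No text says so. Even then some asymmetry remains, because only one arm has cells to miss.

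**Other provisions point towards keeping patients.** Section 7 calls the randomised patients the intention-to-treat population. Section 6 requires survival follow-up, and imaging where possible, after treatment ends for reasons other than progression. Section 4 counts patients with no post-baseline scan as non-responders. The termination criteria could also cover a patient whose product fails. These show intent, but none ties the PFS analysis to all randomised patients or says that elimination does not override it. The non-responder rule concerns response, and a patient eliminated first would not reach it.

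**The prognostic link is weak.** This stands in part. Contamination failures have no stated tie to PFS. Section 1 compares HCC patients with the normal population rather than with each other, and the entry limits on white cells and lymphocytes narrow the spread. The bias is therefore conditional.

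**Removing exactly the earliest failures is extreme.** This also stands. The first scan is at week 4 and the first infusion at week 1, so documented progression cannot explain never being infused. Missing all six infusions in 10% to 20% of patients would need a per-infusion failure rate of 0.10^(1/6) = 68% to 0.20^(1/6) = 76% if failures were independent. Failures of one patient's autologous product may well be correlated, which would lower that rate, and criterion 1 may also catch partial courses. With 5% uninfused at 1.5 to 3 times the hazard, the false-win rate is only 0.6–1.1% (HR 0.96–0.98).

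**Stopping for progression is a different route.** Agreed. "CT/MRI examination confirmed the occurrence of PD, according to the imRECIST" is a termination criterion, and none of the bias above relies on it.

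**Conclusion.** The concern holds, and the plan must be changed. The defect does not depend on any assumed number: the primary analysis population is undefined, and the only exclusion rules given act on one arm and conflict with the only population named. The size of the bias does depend on assumptions. If a few early failures leave TAE-iNKT, the false-win rate at two-sided 0.01 rises from about 0.7% to between 1.0% and 2.0% in the moderate scenarios, with apparent HRs of about 0.84 to 0.95, and to 4.7% in the upper case of six. Removal unrelated to prognosis costs some precision but gives no bias; removal of good-prognosis patients would bias against iNKT. Since the plan states neither how many will be removed nor how they will be chosen, none of these outcomes can be ruled out beforehand.

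**What to change.** Add to Sections 3 and 7: *PFS, OS, ORR, DCR and QoL are analysed in all randomised patients by allocated arm, whether or not iNKT cells were infused.*

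- Keep patients without a post-baseline tumour assessment in the ORR and DCR denominators as non-responders. For time-to-event endpoints, count deaths as each endpoint defines and otherwise censor such patients by one rule that is the same in both arms.
- Confine the elimination criteria to a labelled per-protocol sensitivity analysis. Use criteria that either arm can meet or fail, such as receipt of planned TAE, applied before lock by people blind to outcome. Such a set will not measure adherence to iNKT; any summary of infused patients alone should be labelled descriptive.
- Name the safety population separately, since criterion 1 also refers to the safety evaluation.
- Report the number excluded and the reasons, by arm.

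The cost is protocol and SAP wording plus a short blinded review for the per-protocol set. No patient's treatment changes. The price is a slight dilution of the estimated effect by uninfused patients.
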